Obtaining informed consent. Preliminary conversations with our university IRB have confirmed that, like our other projects, this project will also likely qualify for a waiver of parental consent for minors, based on minor participants' ages (16-17) and the sensitive nature of the topic wherein participants may incur risk if participation is disclosed to a parent. Participants will be asked to consent to project participation as adults. During the consent process, participants can contact the project team with any questions or concerns. The consent process will describe the 2 arms of the study and let them know that after they complete the baseline survey, their assignment to a particular arm will be random. After reading the consent, participants will be asked follow-up questions to verify comprehension.

Consent

Once the identity is confirmed, the respondent will be sent a unique link (exclusive to that participant) to the consent. Once they have read the consent (which they can scroll up or down for review) they will be asked to electronically sign the form in a signature box if they consent. The participant can take as long as they would like to review the consent or discuss with others. They are able to click on the consent link at a later time if they want to think about their participation. If they consent, we will ask them to write or type their name indicating they agree to an electronic signature and that they consent. We include as a part of the consent that they can take a screenshot or video screen recording of the signed consent form for their

records, or they can request a copy be sent to them by email or USPS. We will ask them for a mailing address (optional, unless they request a USPS-delivered signed consent), and social media handles. These latter contact data are helpful as backup for multiple options to contact participants over the course of the 12 month study should cell number and email no longer work. If they do not consent, they will not be able to participate in the study.

The contact information and consenting signature will be stored in a secured database separate from survey data, and accessible only by project staff.

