Assignment methods. Once recruited and consented, eligible AIAN young women will complete the baseline survey, and asked to download the NWC app. Once they have done this, the app will immediately electronically randomize the participant to either NWC or the comparison condition. That is, the two interventions are accessed through the same app – once the participant registers to download the app, she will be randomly assigned one arm or the other. Figure 2 shows participant flow through the proposed project.

Progression of NWC. Because of the electronic mode of administration, participants can progress through each session at their own pace. We will provide electronic reminders if timely progression of the app has not been demonstrated.

Counterfactual intervention. We will provide young women in the comparison arm an engaging online intervention which is independent of our outcomes of interest. The focus will be on life skills including social media safety, budgeting, resume building, and career development.

Participant tracking methods. Participant tracking involves two sets of processes. The first is through screening and enrollment and then survey completion. The second centers on downloading the app and progression through the other surveys in a timely way. 1) On the screening survey, once participants are considered eligible, they will be required to provide their name, phone number, birth month and year, email address, and a second email address (optional). A second email is useful to keep in contact participants in case a primary email is closed. Once a participant has been determined eligible and has read and signed the consent form, we also request mailing address and social media handles, again, useful contact information to track participants over time since at this young age, contact information can change frequently. 2) During the registration process for the app, participants use an email address to register (the registration email is the link to the survey data, to track which participants downloaded and engaged in the app). Through the intervention stage, progress in NWC will be tracked electronically. We will send reminders to young women who have not completed a survey in a timely way (we allow 2 weeks). We will follow up with personal texts, emails, phone calls, or private social media contacts provided, up to 4 times, as necessary.

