Fidelity. Since intervention content will be administered electronically, we anticipate full fidelity. We expect full adherence, and we will be able to monitor closely progress towards this goal. However, we will track occurrences of technological challenges (e.g., lost devices, or navigational issues), or other unanticipated events with respect to the intervention content delivery.

Post-intervention follow-up retention plans. After the intervention, when surveys are months apart and risk of attrition is high, we have integrated additional retention plans. Every two months, we will offer a small

incentive (e.g., \$10 gift card) to participants who confirm their contact information.

Throughout the project, we will use electronic data to monitor study participation. As data are accrued across the rolling sample, we will use electronic data to monitor sample intake, responses rates, and baseline equivalency.

RCT timing. Recruitment will begin PY3 (see "Timeline," below). We anticipate a rolling recruitment across 2 years. This roll-out will allow sampling strategy adjustment as needed.

Procedures/modes of data collection. Once IRB approvals are obtained, we will begin implementation. We will use the University's Qualtrics survey system, a HIPAA-compliant and secured software for research which can be optimized for smartphones or other devices. As noted above, eligible participants who provide consent will be sent a unique URL to complete a baseline survey. Through the tracking software, we will issue additional URLs for follow-up surveys at the appropriate time. Participants will be compensated \$25 for baseline and the first post-intervention survey, increasing to \$35, \$40, and \$50, respectively, for each of the 3 follow-up surveys. Participants will not be re-consented at each survey point; still, at each survey, participants will be reminded that participation is voluntary, and they can decline participation at any time.

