Intervention and survey progression. After the baseline survey, participants will be asked to download the app using their email and a password, so we can track their registration and ultimately link app use with survey data (e.g., to check number of sessions responded engaged in). We will incentivize the app download with a small e-gift card (\$10). Once registered, the app will randomize participants and they can immediately begin their first intervention sessions (NWC or counterfactual). Once participants have progressed through their respective programs, each will be given an additional small e-gift card (\$10), and, 2 months later, a URL for the first posttest. Similarly, at 6 and 12 months after program completion, each will be sent URLs to complete a survey.

We will regularly monitor electronic reports of progress through the intervention (for NWC), and survey completion progress for follow-up (both arms). Survey data will be routinely checked by the Data Management team for any problems, inconsistencies, or missing data. They will routinely summarize response rates for each survey, and by arm. If response rates are low, or unbalanced by arm, Drs. [name] and [name] will identify possible causes, their solutions, and quickly implement changes to rectify deficiencies.

D. Recruitment

The primary method of recruitment will be through multiple social media platforms. Specific recruitment activities will vary across the platforms, but will typically include posts to promote the program and study. We will also use seed recruitment, and encourage AIAN young women participants to invite their peers and family members to sign up for the program (i.e., chain referral, up to 3).

We will ask the participants enrolled in the study to follow our page on Instagram, share our recruitment post on their Instagram page and tag us in that post. This strategy will amplify our recruitment post among their followers (who may be similarly eligible) and encourage participation in our study (as the recruitment post will have come from a trusted source). This is completely voluntary and the recruitment post does not require participants to disclose any personal health information.

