G. Data Analysis Plan:

All intervention effectiveness analyses will be based on an intention-to-treat approach. For continuous outcomes (frequency/quantity indices of alcohol) and mediational outcomes (alcohol and contraceptive self-efficacy), we will estimate a series of latent growth curve models (LGCM) in Mplus to assess the effect of intervention exposure on the trajectories of those outcomes over the study period. The "normative" trajectory of an outcome is estimated for the comparison group before estimating the same trajectory among those exposed to the intervention. The third step estimates the degree to which the normative growth trajectory is altered by intervention exposure. On the fourth and final step, the interaction between intervention exposure and pre-intervention status on the outcome is tested. This permits an assessment of the differential effectiveness of the intervention as a function of baseline levels of the outcome variable.

For dichotomous outcomes, Latent Markov Models (LMM) will be used to evaluate transitions between behavioral states (e.g., sexually active to abstinent) throughout follow-up. 166,167 Intervention status is modeled as a time-invariant covariate; its effect on the transition probabilities is estimated freely. Effectiveness is indicated if those in the intervention have significantly lower probabilities than the controls of transitioning out of the abstinence state and significantly higher probabilities of transitioning out of the sexually active state. LMM may also reveal that early sexual experience among control group participants predicts sexual activity across the course of the study but that this relationship is interrupted among intervention participants. Other moderators of intervention effectiveness will also be explored (e.g., enculturation).

H. Summarize Knowledge to be Gained:

If successful, the overall study will generate evidence of NWC effectiveness for AEP prevention by demonstrating: 1) increased effective contraceptive use or sexual abstinence among urban AIAN young

women; 2) decreased or eliminated alcohol use in urban AIAN young women who drink; and 3) maintained abstinence (sexual or alcohol) among those who have this as their goal. If successful, the project will also provide vital information about the feasibility of mHealth interventions for reaching urban AIAN young women or other urban AIAN populations who might otherwise not access health information or interventions

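### Does paying for five surveys while dating only four leave the trial's follow-up schedule undefined?

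*Combined protocol and SAP*

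**What the plan says.** Two neighbouring paragraphs of section IV.C of the protocol describe the surveys.

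- **Procedures/modes of data collection** sets the payments: $25 "for baseline and the first post-intervention survey, increasing to" $35, $40 and $50, "respectively, for each of the 3 follow-up surveys".
- **Intervention and survey progression** sets the dates. After baseline and the app sessions: "Once participants have progressed through their respective programs, each will be given an additional small e-gift card" and, "2 months later, a URL for the first posttest". It then continues: "Similarly, at 6 and 12 months after program completion, each will be sent URLs to complete a survey".

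Three other places touch the point without settling it. The Consent paragraph explains that backup contact details help the team to "contact participants over the course of the 12 month study". The Assignment methods paragraph says "Figure 2 shows participant flow through the proposed project", and the RCT timing paragraph refers to a Timeline; neither display is reproduced in the available text. Section IV.G (Data Analysis Plan) models "the trajectories of those outcomes over the study period" and the transitions between behavioural states, and gives no number of surveys.

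**The concern.** Read in sequence, the two paragraphs do not agree. The first implies four surveys after baseline and the second dates three. If the survey paid at $25 after the intervention is the one at 2 months, three follow-up payments are left for only two dates. If the three follow-ups are months 2, 6 and 12, the $25 survey must come earlier, but the text dates nothing there and describes the 2-month survey as the first of the posttests.

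This could matter in two ways. Survey links, reminders and response-rate summaries are organised survey by survey, so staff need to know how many there are. The analysis in section IV.G also takes its time points from the survey schedule: four surveys give three intervals for the Markov models and five give four. If the schedule were truly open, the measurement occasions entering the growth curves would be open too.

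**Working it through.** No sample-size or power figure is involved. The check is a count, followed by a test of each way to reconcile the two paragraphs.

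**Counts**

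| | Payment paragraph | Schedule paragraph |
|---|---|---|
| Baseline | 1 | 1 |
| After baseline | 1 + 3 = 4 | 1 + 2 = 3 |
| Total | 5 | 4 |
| Intervals between surveys | 4 | 3 |

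**Readings**

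1. *The $25 post-intervention survey is the 2-month one.* Months 6 and 12 remain, which is two dates for three payments. Shortfall: 3 − 2 = 1 date.
2. *The $25 survey is taken at programme end and the three follow-ups are months 2, 6 and 12.* All five payments have a survey, and all four printed dates (baseline, 2, 6, 12) are used. The programme-end survey is undated in the visible text, and the label on the 2-month survey is then loose. The sentence about a gift card at programme completion does not exclude a survey at that moment.
3. *There is no separate post-intervention survey.* The three follow-ups match months 2, 6 and 12, and one $25 payment has no survey of its own.
4. *Another incentive fills the gap.* It cannot. The payments for downloading the app, finishing the programme and confirming contact details are separate gift cards not tied to a survey.

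No reading satisfies every word of both paragraphs. Reading 2 needs only one label corrected. All the readings keep baseline and months 2, 6 and 12; they differ only on whether one further survey exists.

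**Money**, reading $25 as the amount for each of the first two surveys. Five surveys: 25 + 25 + 35 + 40 + 50 = $175 per participant who completes all of them. If one payment falls away, the total is 175 − 25 = $150, 175 − 35 = $140, 175 − 40 = $135 or 175 − 50 = $125. Reading 3 gives the $150. The difference is one payment, $25 to $50 per participant.

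**Analysis.** Take a straight-line growth model in one arm with T surveys. It has T means and T(T + 1)/2 variances and covariances to fit. Its parameters are 2 growth means, 3 growth variances and covariances, and T residual variances.

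- T = 4: 4 + 10 = 14 moments against 2 + 3 + 4 = 9 parameters, leaving 5 degrees of freedom.
- T = 5: 5 + 15 = 20 moments against 2 + 3 + 5 = 10 parameters, leaving 10 degrees of freedom.

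The model meets this counting condition either way. The Markov models run over three or four intervals. The enrolment target of 700 and the final 525 in the third specific aim are stated without reference to the number of surveys.

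**The case for a change.** The strongest case for acting is that this is a conflict between two visible sentences and not just missing detail. Even if the participant-flow figure showed a programme-end survey, the schedule paragraph would still call the 2-month survey the first posttest. Counting the post-intervention survey as one of the three follow-ups does not help, because it would then be priced at both $25 and $35. Reminders and response rates by arm cannot be produced for an undated survey. An unsettled set of surveys could also, in principle, let the analysts choose time points after seeing data. One table would cure all this at almost no cost.

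The count stands, and so does the point about the label. The rest is weaker. The paragraphs are not instructions that exclude each other, because the schedule paragraph does not claim to be a complete list and reading 2 can be carried out as written apart from a name. The figure and the Timeline may already date the extra survey, and their absence from the available text is no fault of the plan. The worry about choosing time points has little substance: the surveys are issued prospectively through the survey system, so the set collected is fixed by the links sent, and a trajectory over the study period would naturally use all of them. Asking section IV.G to list its time scores is a separate request for more analysis detail and does not follow from a payment sentence. The remark about a 12-month study is an aside on contact details and fixes no survey.

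**Conclusion.** The mismatch is real and small: five surveys paid, four dated, a difference of one link and one payment of $25 to $50 per participant. It is a clerical inconsistency between a payment list and a survey label, which the survey system's programmed schedule, the participant-flow figure or the Timeline would be expected to resolve. It is not shown to bias an estimate or to alter the sample size, power, a safety rule or a conclusion, and the planned models accommodate either count. No change to the plan is called for.

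This rests on two assumptions. The four dated surveys are taken as printed, which every reading preserves. The analysts are assumed to use every survey actually collected, at the time it was scheduled. Which reading the sponsor intended cannot be established from the visible text, and the conclusion does not depend on it.

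### The 2-, 6- and 12-month surveys are counted from programme completion, and the readable text gives no survey date to randomised women who do not finish

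*Combined protocol and SAP*

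**What the plan says.** The order of events is set out in Section IV.C.

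- **Randomisation.** Under Assignment methods, after the baseline survey and app registration, "the app will immediately electronically randomize the participant to either NWC or the comparison condition".
- **Programme.** Under Progression of NWC, "participants can progress through each session at their own pace". Electronic reminders are promised for slow progress; no deadline is given.
- **First posttest.** Under Intervention and survey progression, "Once participants have progressed through their respective programs, each will be given an additional small e-gift card" and then "2 months later, a URL for the first posttest".
- **Later surveys.** The next sentence reads "Similarly, at 6 and 12 months after program completion, each will be sent URLs to complete a survey".
- **Monitoring.** The same part registers participants by email so that the team can "ultimately link app use with survey data", including a check on how many sessions were used. On survey returns it says "They will routinely summarize response rates for each survey, and by arm", and it promises corrective action if rates are low or differ between arms.

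Section IV.G puts every effectiveness analysis on an intention-to-treat basis. Fidelity (IV.C) anticipates complete adherence, whereas Section IV.F concedes that this population's engagement with electronic interventions is not yet fully known. Assignment methods also states that "Figure 2 shows participant flow through the proposed project"; that figure, and the Timeline cited under RCT timing, are not in the text supplied.

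**The concern.** The survey clock starts at an event that happens after randomisation, is under the participant's control and may never happen. A woman who registers, is randomised and stops partway has no stated date for any follow-up survey. If staff apply the text literally, she contributes baseline data and nothing else to an analysis that is meant to include everyone randomised.

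The data at 2, 6 and 12 months would then come from women selected by finishing one of two programmes with different content. If finishing differs between arms and is related to drinking or sexual risk, the followed-up groups are no longer comparable by randomisation. The comparison could show a benefit that is not there or hide one that is. The planned growth and Markov models use baseline or prior state and can remove the part of the selection which those data explain, but baseline would be the only outcome data on non-finishers.

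There is also a loss of numbers whatever the bias: the completion rate would cap how many women can have follow-up data at all.

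**Working it through.** **Step 1: look for any survey date that does not depend on finishing.** Besides the sentences quoted above, three places in Section IV.C touch on timing.

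| Place | What it gives | Does it date a survey for a non-finisher? |
|---|---|---|
| Consent | A study length of 12 months | No; no starting point is named |
| Procedures/modes of data collection | Follow-up links to be issued in due course by the tracking software | No; no date or trigger |
| Participant tracking methods | Reminders after a two-week allowance for a survey not completed | No; it sets no date for sending a survey |

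The 2-month sentence speaks of having progressed through the programme, and the next sentence opens with a word of likeness and names programme completion. All three dated surveys therefore share the same starting event. Loosely, progressing through might mean that the programme period has elapsed, but no such period is stated, so a non-finisher would still have no date.

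**Step 2: the plan's own numbers.** Specific Aim 3 gives 700 recruited and a final N of 525. 525/700 = 0.75, so the plan implies 75% retention. It states neither a completion rate nor a dropout rate, and does not define what the 525 counts.

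**Step 3: what the completion trigger would require.** Assumptions, none of them settled by the documents: all 700 are randomised; only finishers are surveyed; the 525 are women with follow-up data. With completion rate c (an assumed range),

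response needed among finishers = 525 / (700 × c).

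| Completion c | Finishers, 700 × c | Response needed |
|---|---|---|
| 90% | 630 | 525/630 = 83.3% |
| 80% | 560 | 525/560 = 93.8% |
| 75% | 525 | 525/525 = 100% |
| 70% | 490 | not reachable; at most 490 |

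If every randomised woman is surveyed, the requirement is 525/700 = 75.0% whatever the completion rate.

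**Step 4: direction of bias.** The documents give no completion rate by arm and no risk by completion status, so no size can be computed. Bias arises only if completion differs by arm, in amount or in who finishes, and is related to risk. If completion is equal and non-differential, there is no between-arm bias. The sign depends on which programme is finished more often and by whom.

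**The case against.** The strongest reply is that this is silence, not a rule of exclusion. A participant-flow figure is the natural home for a rule on non-finishers, and it cannot be read here; nor can the Timeline. No text says that non-finishers go unsurveyed. The intention-to-treat commitment and the plan to count sessions used both suggest that women with partial exposure were expected in the survey data. Fidelity expects complete adherence, which may explain why only the finisher's path is written down. The comparison programme is meant to be engaging, sits in the same app and carries the same completion gift card. Finally, the plan undertakes to act on low or unbalanced response.

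Most of this stands as a limit on the claim. A reader might infer that the plan restricts follow-up to finishers, or that the trial estimate will be biased. The documents support neither: the first is a literal reading of a sentence that may describe only the expected path, and the second needs completion and risk rates that they do not contain.

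It does not remove the point. Session counts and an intention-to-treat label set no survey date. The expectation of complete adherence sits beside the admission in Section IV.F that engagement is uncertain. Reminders and gift cards make stopping less likely but do not date a survey for a woman who still stops. The promise to correct unbalanced response names no denominator: if rates are computed among women who were sent a link, they can look high and balanced while non-finishers go uncounted.

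Counting from completion is also a legitimate choice for measuring persistence after the programme. Fixed dates from registration would give that up in part, because a slow participant could be surveyed before she finishes. That is a trade-off, not a correction.

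**Conclusion.** The point holds as a gap that should be fixed, with medium confidence. As far as the readable text goes, all three dated outcome surveys start from a self-paced, post-randomisation event without a deadline, and randomised women who do not reach it have no survey date. Read literally, this conflicts with the intention-to-treat commitment.

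The size that can be stated concerns numbers, not bias. Under the three assumptions in the working, reaching 525 needs 83.3% response at 90% completion and 93.8% at 80%, and is impossible below 75%, against 75% if everyone is surveyed. No magnitude of bias and no error rate is claimed.

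The conclusion would reduce to a request for clearer wording if Figure 2 or the Timeline already dates surveys for non-finishers.

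**What to change.** In Section IV.C, Intervention and survey progression:

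1. Keep completion-based timing, but state one maximum time after app registration, the same in both arms, at which the survey clock starts for anyone who has not finished.
2. State that all follow-up surveys go to every randomised participant, whatever her progress.
3. Report response rates by arm with all randomised participants as the denominator, so that the promise to act on imbalance has something to work on.
4. If Figure 2 or the Timeline already contains such a rule, repeat it in this text.
5. Reconcile the number of post-baseline surveys. The payment text under Procedures/modes of data collection can be read as four (a first post-intervention survey plus three follow-ups); the schedule dates three.

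**Cost.** One protocol sentence and a change to the survey trigger. Some women will be surveyed without having finished, so for them the first posttest does not measure persistence after the programme.

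Extra incentives per non-finisher depend on item 5: $25 + $35 + $40 = $100 or $35 + $40 + $50 = $125 for three surveys, and $25 + $35 + $40 + $50 = $150 for four. If all 700 are randomised and every non-finisher responds, the maximum is:

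- 90% completion (70 non-finishers): $7,000 to $8,750 for three surveys, or $10,500 for four.
- 80% completion (140 non-finishers): $14,000 to $17,500 for three surveys, or $21,000 for four.

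If surveys in fact already go to everyone, there is no added incentive cost.

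### Program progress is monitored for the NWC arm only, yet program completion releases the follow-up surveys in both arms, so survey timing and follow-up can differ by arm

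*Combined protocol and SAP*

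**What the plan says.** Section IV.C, Intervention and survey progression, gives each kind of monitoring its own arm scope: "We will regularly monitor electronic reports of progress through the intervention (for NWC), and survey completion progress for follow-up (both arms". The paragraph on participant tracking methods in the same section names only one program: "Through the intervention stage, progress in NWC will be tracked electronically". The comparison program has its own short paragraph (Counterfactual intervention), which mentions neither tracking nor reminders.

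Both programs sit in one app, which randomises a woman when she registers. The paragraph headed Progression of NWC says "participants can progress through each session at their own pace" and adds "We will provide electronic reminders if timely progression of the app has not been demonstrated". No maximum program duration is given.

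The trigger for outcome assessment is the same in both arms: "Once participants have progressed through their respective programs, each will be given an additional small e-gift card", with the first posttest link following 2 months later. The later surveys follow the same clock: "Similarly, at 6 and 12 months after program completion, each will be sent URLs to complete a survey". Response rates are to be summarised for each survey and by arm, and the investigators act "If response rates are low, or unbalanced by arm".

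**The concern.** In many trials, progress through the program is only a measure of adherence. Here it also starts the outcome schedule: until a woman finishes her program, no follow-up link is due. Completion happens after randomisation, and study staff can influence it. If staff watch for stalled progress in one arm and not the other, the arms may finish at different rates and after different delays. Part of any observed difference could then reflect when, and in whom, outcomes were measured and not what the program did. Section G promises an intention-to-treat comparison of trajectories and of transitions between behavioural states, and both depend on comparable timing and follow-up.

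**Working it through.** **1. Scope of each procedure, as written.**

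| Procedure (section IV.C) | Arm scope in the text |
|---|---|
| Regular review of intervention progress | NWC |
| Electronic tracking in the intervention stage | NWC named, comparison program not named |
| Reminders for slow progression | Unclear: placed under the NWC heading, but refers to the app, which both arms share |
| Review of survey completion | Both arms |
| Reminders for overdue surveys (2 weeks allowed, up to 4 contacts) | Not restricted |
| Release of survey links at 2, 6 and 12 months after completion | Both arms |

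The asymmetry that the text clearly supports is therefore in monitoring. The payment schedule implies four post-baseline surveys (a first post-intervention survey and three follow-ups), but triggers are given for three, so the point is verified for those three.

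**2. Whether the other safeguards reach the gap.** Reminders for overdue surveys do not help a woman who has not finished her program, because no follow-up survey is yet due from her. By-arm response summaries act only after an imbalance appears and do not address calendar timing. The plan does not say whether women never sent a link count in their denominator. Nor does it say that a corrective change must be made in both arms.

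**3. The plan's own figure.** Specific aim 3 gives 700 recruited and a final N of 525. 525 / 700 = 0.75, an implied loss of 25%. The two figures are consistent; no split by arm is given.

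**4. Illustration: unequal follow-up.** Assumptions: 1:1 allocation (350 per arm), 75% retained overall, and the same risk gap d between unreached and reached women in both arms. Let p be the true prevalence of the risk state in an arm and m the share not reached. The prevalence among reached women is then p − m × d, so the observed arm difference shifts by (difference in m) × d.

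- 80% v 70% retained: 350 × 0.80 = 280 and 350 × 0.70 = 245 (total 525). Difference in m = 0.30 − 0.20 = 0.10. With d = 0.10 to 0.20, the shift is 0.01 to 0.02, or 1 to 2 points.
- 85% v 65% retained: 350 × 0.85 = 297.5 and 350 × 0.65 = 227.5 (total 525). Difference in m = 0.35 − 0.15 = 0.20. With the same d, the shift is 0.02 to 0.04, or 2 to 4 points.

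With equal retention the difference in m is zero and so is the shift.

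**5. Illustration: unequal timing.** If one arm completes later by a given number of weeks, all its survey dates move by that lag (weeks / 4.345 = months), measured from the other arm's completion.

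| Assumed lag | Months | Nominal 2, 6 and 12 months become | Lag as share of the 2-month interval |
|---|---|---|---|
| 4 weeks | 0.92 | 2.9, 6.9, 12.9 | 46% |
| 8 weeks | 1.84 | 3.8, 7.8, 13.8 | 92% |
| 12 weeks | 2.76 | 4.8, 8.8, 14.8 | 138% |

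The shift matters most, in proportion, at the first posttest.

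**The case against.** The strongest reply is that the wording concerns who reads progress reports, not who is contacted. Both programs run in one app, which the protocol itself calls the NWC app, so some mentions of NWC may mean the app and not the arm. Completion has to be detected in both arms to release gift cards and links. App use is to be linked to survey data without naming an arm, and the adherence monitoring under Fidelity names no arm. Survey reminders, two-monthly contact updates and payments are written for participants generally, and response rates are reviewed by arm.

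Much of this stands, and it limits the point in four ways.

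- A reader might infer that comparison women will receive fewer prompts. The documents do not support that: the reminder sentence refers to the shared app, and its scope is unclear.
- A reader might infer that the asymmetry would do the same harm however surveys were triggered. It would not. If links were timed from randomisation, slow completion in one arm would neither move its survey dates nor withhold its links.
- A reader might infer that a missing-at-random assumption in the plan is undermined. Section G states no missing-data assumption.
- A reader might take the point shifts as estimates, or assume that the comparison arm would be the one worse followed. The documents support neither.

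The reply does not remove the core. The sentence sets NWC against both arms explicitly, so it is hard to read its NWC as the shared app. That completion can be detected in both arms shows that equal monitoring is feasible, not that it is planned. Full adherence is an expectation; section F concedes that engagement with electronic interventions in this population is not yet fully known.

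**Conclusion.** The concern holds as a statement about the written procedure. Oversight of the step that opens outcome assessment is specified for one arm, while that step releases the 2-, 6- and 12-month surveys in both. Survey timing and follow-up can therefore differ by arm; the documents do not show that they will, or which way.

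The range of 1 to 4 points is an illustration. It rests on 1:1 allocation, 75% overall retention, chosen retention splits and a common reached-versus-unreached risk gap of 10 to 20 points. It also takes the whole retention gap as given, and nothing in the documents says what share would come from unequal monitoring. The lags of 4 to 12 weeks are likewise assumed. No sample-size figure changes.

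The correction should be made because it is specific and nearly free. It is a partial remedy: two self-paced programs with different content could still be completed at different rates while completion remains the trigger.

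**What to change.** - In Intervention and survey progression, and in Participant tracking methods, state that program progress is monitored in both arms.
- State that reminders for slow progression follow the same schedule, with the same maximum number of contacts, in both arms.
- State that any mid-trial change made to improve retention applies to both arms at the same time.
- Report by arm the proportion completing the program and the days from randomisation to each survey. Count women never sent a link in the denominator of the response rates.

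The cost is a wording change, some extra automated messages and minor logging in an app that already serves both arms. The remaining exposure comes from the completion trigger itself, and the by-arm reporting would make it visible.
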